7.3 Data Controller

The University of Edinburgh and NHS Lothian are joint data controllers along with any other entities involved in delivering the study that may be a data controller in accordance with applicable laws (e.g., the site)

The Investigator will maintain source documents for each patient in the study, consisting of case and visit notes (hospital or clinic medical records) containing demographic and medical information, laboratory data, electrocardiograms, and the results of any other tests or assessments. All information relevant to a participant's general medical history on CRFs must be traceable to these source documents in the patient's case notes. The CRF will be used as source data for other information.

A data management system will be provided by ECTU. The study system will be based on the protocol and the CRF for the study and individual requirements of the Investigators. Development and validation of the study database and QC and extraction of data will be done according to ECTU procedures. Extracts for analysis will be based on the dummy data tables provided by the study team. Core laboratory data will be inputted directly from the individual sites into the ECTU built database.

The eCRF will not collect more information than is required to meet the aims of the study and to ensure the eligibility and safety of the participant. The CRF will be used as source data but data relevant to a participant's general medical history will be recorded also in the electronic case notes.

7.4 Data Breaches

Any data breaches will be reported to the University of Edinburgh and NHS Lothian Data Protection Officers who will onward report to the relevant authority according to the appropriate timelines if required.

8. STATISTICS AND DATA ANALYSIS

8.1 SAMPLE SIZE CALCULATION

With a sample size of 36 per group we would be able to detect a difference of 0.76 log unit in the change in bacterial load between treatment arms assuming a common standard deviation of 0.98 log units based on a two-sided, two-sample test with 5% level of significance and 90% power¹⁹. A 10% drop out rate increases this to 80 patients (40 per group).

8.2 PROPOSED ANALYSES

Analysis

Full details of the statistical analysis will be detailed in a separate Statistical Analysis Plan developed prior to examination of any accumulated trial data. A summary of the planned analysis is given below.

Results will be presented broken by treatment allocation. Where data is categorical number and percent will be presented however where data is continuous descriptive statistics including mean, standard deviation (sd), median, q1, q3, min, max will be presented. As this is a proof-of-concept study we will present descriptive statistics for markers of interest by treatment arm at each time point as well the baseline to 1-year change. No covariates are planned to be adjusted for these analyses.

Where responses are continuous for example the level of change in cfu, comparison between groups will be made using a two-sample t-test and results of this will be presented accompanied by the mean and 95% for the difference between groups. We will present the time to first exacerbation using a Kaplan-Meier survival curve stratified by treatment allocation and present this will the accompanying log-rank statistic.

Where responses are binary i.e., presence of clinically significant change in cfu, comparisons between groups will be made using a binomial test for the comparison of proportions and accompanying this we will present the difference in proportion and 95% CI for the difference.

The number of participants experiencing adverse events and serious adverse events will be reported as well as the number of events per participant. Comparison will be made between treatment arms.

As information on AE/SAE will be captured during the washout phase prior to any dosing with study drug we will present this information separately for AE/SAE occurring prior to the first dosing and AE/SAE occurring after the first dosing.

Dropouts during the study will be reported and where available a reason for dropout will be captured. The dropout rate will be compared across both treatment arms

16S and ITS data: we will summarise and visualise microbial and fungal community compositions using ordination techniques/PERMANOVA-tests, allowing for global comparisons between groups. To compare alpha diversity between samples, we will look at the richness, as well as the Shannon diversity index. Beta diversity, which represent the between sample diversity, will be investigated using the Bray-Curtis dissimilarity. In addition, using a data-driven, unsupervised clustering approach we will discern profiles that will subsequently be linked to host phenotypes, enabling us to identify microbial structures associated with host infection susceptibility. Depending on the distribution of data, we will use either classical regression (MetagenomeSeq) or a machine learning technique (randomForest) to identify microbes driving differences between patient groups.¹⁴⁻¹

Metagenomic sequencing: Microbial DNA will be isolated and processed as previously described. The For bacterial community profiling, the V4 hypervariable region of the 16S-rRNA gene was amplified using barcoded primer pair 533F/806R. To profile the fungal community, we will target the ITS1 region using a two-step protocol as described by Illumina (Fungal sequencing and classification with the ITS Metagenomics Protocol) with some modifications. Amplicons will be quantified using PicoGreen (Thermo Fisher Scientific, Invitrogen, Eugene, OR, USA) and pooled in equimolar amounts. Amplicon pools of samples and controls are sequenced using the Illumina MiSeq platform (San Diego, CA, USA).

Bioinformatic processing: Bioinformatic processing of 16S reads will be performed as previously described¹⁹ and included quality filtering/trimming, error correction, read assembly and binning reads in OTUs of 97% similarity. Bacterial sequence variants will be annotated using the Silva database (version 119).²⁰ Taxonomic assignment of fungal sequence variants will be annotated using the UNITE QIIME release database version 01.12.2017 and the RDP classifier in QIIME version 1.9.²¹

Quality control: To control for contaminating DNA we will process DNA isolation and PCR controls, and use mock communities as positive controls. Following, the *decontam* R-package²² will be used to identify contaminating sequence variants for 16S- and ITS-based data separately.

Quantifying biomass: We will quantify the fungal DNA concentration using Picogreen. For bacteria, we will use qPCR.

Statistical/data analysis: All analyses will be performed in SAS v9.4 or later (SAS Institute Inc., Cary, NC, USA.) or R version 3.6.3 within R studio version 1.2.5033 (Boston, MA) or a later version

We will use the packages vegan, phyloseq²³, microbiome²⁴, and ggplot2²⁵ for our microbial community structure (microbiota) analyses.

For both datasets, the relative abundances will be calculated by dividing the sequencing reads assigned to different taxa by the total number of reads per sample.

Benjamini-Hochberg (BH) adjusted P values (q values) will be used where appropriate. A P value and a q value of 0.05 will be considered significant.

All patient samples will be subjected to a similarity-based, unsupervised hierarchical clustering approach based on absolute abundances to identify community state types/clusters.

For comparisons of group differences, a one-way analysis of variance, Wilcoxon rank-sum test, Kruskal-Wallis test, or chi-square test will be used where appropriate depending on the variable(s) tested.

Group differences in diversity will be calculated using Wilcoxon tests and linear mixed-effect models. Associations between group and overall microbiota composition will be analysed using the adonis2 function (vegan package⁶⁹), based on permutational multivariate analysis of variance (PERMANOVA)-tests. Differences between groups on the lowest taxonomic annotated level (OTU) will be tested using the metagenomeseq package in R studio or the machine learning method Random Forest, depending on the distribution of data in our cohort.

9. PHARMACOVIGILANCE

The Investigator is responsible for the detection and documentation of events meeting the criteria and definitions detailed below.

Full details of contraindications and side effects that have been reported following administration of the IMP can be found in the relevant Summary of Product Characteristics (SPC) Booklet.

Participants will be instructed to contact their Investigator at any time after consenting to join the trial if any symptoms develop. All adverse events (AE) that occur after informed consent until the final follow-up assessment must be recorded in the Case Report Form (CRF) or AE log. In the case of an AE, the Investigator should initiate the appropriate treatment according to their medical judgment.

9.1 **DEFINITIONS**

An **adverse event** (AE) is any untoward medical occurrence in a clinical trial participant which does not necessarily have a causal relationship with an investigational medicinal product (IMP).

An **adverse reaction** (AR) is any untoward and unintended response to an IMP which is related to any dose administered to that participant.

A serious adverse event (SAE), serious adverse reaction (SAR). Any AE or AR that at any dose:

- results in death of the clinical trial participant; is life threatening*
- requires in-patient hospitalisation or prolongation of existing hospitalisation;

- results in persistent or significant disability or incapacity;
- consists of a congenital anomaly or birth defect;
- results in any other significant medical event not meeting the criteria above.

*Life-threatening in the definition of an SAE or SAR refers to an event where the participant was at risk of death at the time of the event. It does not refer to an event which hypothetically might have caused death if it were more severe.

Any hospitalisation that was planned prior to enrolment will not meet SAE criteria. Any hospitalisation that is planned post enrolment will meet the SAE criteria and will be reviewed by the local PI and if needed by the CI. This is because this is a high-risk exacerbator group that is being dealt with and would naturally be prone to exacerbations and hospital admissions.

A suspected unexpected serious adverse reaction (SUSAR) is any AR that is classified as serious and is suspected to be related to the IMP, that it is not consistent with the information about the IMP in the Summary of Product Characteristics (SPC) booklet or Investigators Brochure.

9.2 IDENTIFYING AES AND SAES

Participants will be asked about the occurrence of AEs/SAEs at every visit during the study. Open-ended and non-leading verbal questioning of the participant will be used to enquire about AE/SAE occurrence. Participants will also be asked if they have been admitted to hospital, had any accidents, used any new medicines or changed concomitant medication regimens. If there is any doubt as to whether a clinical observation is an AE, the event will be recorded.

AEs and SAEs may also be identified via information from support departments e.g., laboratories.

9.3 RECORDING AES AND SAES

When an AE/SAE occurs, it is the responsibility of the Investigator, or another suitably qualified physician in the research team who is delegated to record and report AEs/SAEs, to review all documentation (e.g., hospital notes, laboratory and diagnostic reports) related to the event. The Investigator will then record all relevant information in the CRF/AE log and on the SAE form (if the AE meets the criteria of serious).

Information to be collected includes dose, type of event, onset date, Investigator assessment of severity and causality, date of resolution as well as treatment required, investigations needed and outcome.

9.3.1 Pre-existing Medical Conditions

Pre-existing medical conditions (i.e., existed prior to informed consent) should be recorded as medical history and only recorded as adverse events if medically judged to have worsened during the study.

9.3.2 Worsening of the Underlying Condition during the Trial

Medical occurrences or symptoms of deterioration that are expected due to the participant's underlying condition should be recorded in the patient's medical notes and only be recorded as AEs on the AE log if medically judged to have unexpectedly worsened during the study. Events that are consistent with the expected progression of the underlying disease should not be recorded as AEs.

9.3.3 Adverse Events to be reported on eCRF

For a complete list of the expected adverse reactions and reference safety information of the TEMPESTAS study medication, refer to section 4.8 of each SmPC in the current TEMPESTAS SmPC booklet. To better assess the events that are of special interest to the trial, the following adverse events will also be reported in the eCRF from Baseline until the Final assessment regardless of severity and seriousness:

- Any community respiratory exacerbations of COPD
- Community diagnosed pneumonias
- Any oral infection
- New respiratory conditions detected or diagnosed after study treatment administration
- Signs, symptoms, or the clinical sequelae of a suspected overdose of either study treatment or a concomitant medication any cardiovascular or cerebrovascular events

Laboratory, Spirometry and Vital Signs assessments

Deterioration as compared to baseline in CSP-mandated laboratory values, spirometry values and vital signs should only be reported as AEs if:

- They fulfil any of the SAE criteria, or
- Are the reason for discontinuation of treatment with the study intervention, or
- Are considered to be clinically relevant as judged by the investigator (which
 may include but not limited to consideration as to whether treatment or nonplanned visits were required or other action was taken with the study
 intervention, e.g., dose adjustment or study intervention interruption).

If deterioration in a laboratory value/vital sign is associated with clinical signs and symptoms, the sign or symptom will be reported as an AE and the associated laboratory result/vital sign will be considered as additional information. Wherever possible the reporting investigator uses the clinical, rather than the laboratory term (e.g., anaemia versus low haemoglobin value).

In the absence of clinical signs or symptoms, clinically relevant deteriorations in non-mandated parameters should be reported as AE(s).

Any new or aggravated clinically relevant abnormal medical finding at a physical examination as compared with the baseline assessment will be reported as an AE unless unequivocally related to the disease under study.

Events not listed in this section will be recorded in the patient medical notes.

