2.2.2 Secondary Endpoints

- 1. Change in sputum microbial diversity and microbial biomass (see analyses below for details) ¹³⁻¹⁵ between the two arms.
- 2. **Sputum colour** as assessed by a standardised colour chart- patients are graded as mucoid (clear or grey phlegm, muco-purulent (light yellow or green) and purulent (dark yellow or green) ¹⁸.
- 3. **a) Microbial community composition** (gram negative/positive ratio, abundance of potential pathogens etc.)¹⁴
 - **b) Fungal microbiome**: between the two groups to see if ICS can influence the heterogeneity of the fungal community in terms of absolute and relative abundance.²⁰⁻²¹
- 4. **Spirometry**: forced expired volume in 1 second, forced vital capacity and its ratio and mid expiratory flows (FEF25-75) (attenuation of decline in lung function would be of long-term benefit to patients if found).
- 5. **Quality of Life**: quality of life assessed by the COPD Assessment Tool (CAT) ¹⁶ and St. George's Respiratory Questionnaire¹⁷. Breathlessness is included as part of this questionnaire.
- 6. **Sputum inflammation**: we will assess sputum myeloperoxidase as a measure of neutrophil burden and free elastase activity¹².
- 7. **Serum inflammation**: we will measure white cell count and differential, C Reactive Protein (CRP) and intercellular adhesion molecule 1 (ICAM-1)¹¹ Previous research has shown that at high bacterial loads there is increased ICAM-1¹²
- 8. **Exacerbations**: These would be categorised as
 - *time to the *first moderate or severe exacerbation* requiring treatment with antibiotics and/steroids, **number of exacerbations* (needing antibiotics and/steroids) over 12 months including hospitalisations

*number of participants with radiologically confirmed *pneumonia* over this period.

- 9. **Mortality rate** between the 2 arms of the study groups. Considering the group's overall but also separately broken down by microbe and microbial diversity.
- 10. Safety endpoints: The incidence of all AE and SAE across both treatment arms would be described as well as a safety endpoint. To assess and investigate safety and benefits of a trial design like this, we will also document parameters such as respiratory failure), hospitalised exacerbations (along with other exacerbation data as specified above), and trial dropout due to worsening COPD symptoms as safety endpoints. This would be documented between both the arms of the study.

[figure not shown]

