Pneumonia in patients with COPD Systemic effects of corticosteroids: bone disorders,	Pneumonia is a class concern for any ICS-containing product for the treatment of COPD. In two replicate 12-month studies, in the FF/VI clinical program, in a total of 3,255 patients with COPD who had experienced a COPD exacerbation in the previous year, there was a higher incidence of pneumonia (6%-7%) reported in patients receiving the FF (at strengths of 50, 100, and 200 µg)/VI 25 µg combination than in those receiving VI 25 µg alone (3%). In some instances, these pneumonia events were fatal (including one fatality on FF/VI 100/25 µg dose). Risk factors for pneumonia observed in these studies included current smokers, patients with a history of prior pneumonia, patients with a body mass index <25 kg/m2 and patients with an FEV1<50% predicted. These factors should be taken into consideration when using an ICS in patients with COPD with coexistent bronchiectasis. Pneumonia risk will be important in the benefit-risk assessment for FF/UMEC/VI in COPD patients, hence a robust risk mitigation strategy is being proposed. A decrease in bone mineral density and the risk of fractures is a class	 the protocol (section 3.5) Collection of information on previous history of pneumonia in past 12 months, including hospitalisation at baseline Use of pneumonia electronic Case Report Form (eCRF) All diagnoses of pneumonia (radiographically confirmed or unconfirmed) must be reported as an AE or SAE (if applicable) CXR read required whenever a patient has suspected pneumonia
bone mineral density decrease and associated fractures	and the risk of fractures is a class concern for any ICS-containing product for the treatment of COPD. This is however a very small risk as has been shown in previous studies.	bone systemic corticosteroid effects will be conducted through assessment of reported bone adverse events (Review AE/SAE reports)

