9.5 RECORDING OF AEs

All adverse events for each participant will be recorded on the AE log and will be assigned the appropriate MedDRA Systems Organ Class (SOC) code.

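### Protocol Section 9.3.3 sends unlisted adverse events to the medical notes, against Sections 9, 9.3 and 9.5, so non-serious unlisted events may be missing from the all-AE safety endpoint

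*Protocol*

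**What the plan says.** **All AEs on the CRF or AE log.** The opening of Protocol Section 9 covers all AEs "that occur after informed consent until the final follow-up assessment must be recorded in the Case Report Form (CRF) or AE log". Section 9.3 repeats the destination: "The Investigator will then record all relevant information in the CRF/AE log and on the SAE form", the latter form being for serious events. Section 9.5 says "All adverse events for each participant will be recorded on the AE log", with MedDRA coding. Section 9.2 adds that doubtful observations are recorded. Table 1 has a row for collecting all AE and SAE data, and Sections 6.2 to 6.4 place AEs from Visits 2, 4 and 5 in the eCRF or CRF.

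**A list, and the notes for the rest.** Section 9.3.3 names events of special interest to be reported in the eCRF from Baseline to the Final assessment: community COPD exacerbations, community-diagnosed pneumonia, oral infection, new respiratory conditions, suspected overdose, and cardiovascular or cerebrovascular events. It then says when laboratory, spirometry, vital-sign and examination findings become AEs. It closes with "Events not listed in this section will be recorded in the patient medical notes".

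**Disease worsening.** Section 9.3.2 says "Events that are consistent with the expected progression of the underlying disease should not be recorded as AEs".

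**Use of the data.** Section 2.2.2, item 10, says "The incidence of all AE and SAE across both treatment arms would be described as well as a safety endpoint". SAP 4.6 presents participants with at least one AE/SAE and the number of events per participant, by allocation. It names no data source.

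**The concern.** The protocol gives two destinations for the same event. A non-serious AE outside the 9.3.3 list goes on the log under Sections 9, 9.3 and 9.5, and into the medical notes under 9.3.3. SAP 3.3 runs the analysis on the locked database, and Section 6.9 says that database is filled through eCRFs. Neither document provides for retrieving AEs that sit in the notes, and neither limits the AE tables to the 9.3.3 list. A table labelled as all AEs could therefore leave some out without saying so.

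Some of the events exposed to this gap belong to the steroid-class risks that separate the two arms. For bone effects, the risk table in Section 4.5 relies on "assessment of reported bone adverse events (Review AE/SAE reports"); for ocular effects it gives an exclusion criterion and review of AE/SAE reports. Neither type of event is named in 9.3.3.

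A second ambiguity concerns exacerbations. Section 3.4 selects participants with two or more exacerbations, or at least one hospitalisation, in the previous year. Whether exacerbations count as AEs could therefore drive the AE totals, and SAP 4.6 does not say.

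**Working it through.** The documents give no AE rates and no figure that depends on this rule, so there is no plan figure to reproduce. The main check sets the rules side by side.

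| Event | Sections 9, 9.3, 9.5 | Section 9.3.3 | Result |
|---|---|---|---|
| SAE | CRF/AE log and SAE form | Not affected; 24-hour route in 9.6 | Captured |
| Oral infection, community pneumonia, cardiovascular or cerebrovascular event | CRF/AE log | Listed for eCRF, at any severity | Captured |
| Clinically relevant laboratory, spirometry, vital-sign or examination finding | CRF/AE log | Reported as an AE | Captured |
| Other non-serious AE, e.g. symptomatic bone or ocular event | CRF/AE log | Medical notes | **Conflict** |
| Community COPD exacerbation | Not an AE if expected progression (9.3.2) | Listed for eCRF | **Conflict over AE status** |

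**Does 9.3.3 mean notes instead of the log?** It does not say so outright. Section 9.3.2, however, uses the notes and the AE log as alternative destinations: expected deterioration goes in the notes and reaches the log only if it worsens unexpectedly. Read after that, the closing sentence of 9.3.3 most naturally means the notes in place of the log. If unlisted events also went on the log, the sentence would add little.

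**Would the examination clause catch bone and ocular events?** Not reliably. Section 5.3.1 describes a detailed examination at screening covering the respiratory, cardiovascular, abdominal and dermatological systems. Table 1 otherwise ticks it only for exacerbation visits. Bone or eye symptoms would mostly come from what participants report.

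**Illustration of size (assumed inputs, not from the documents).** Let AE counts be Poisson with mean m per participant, and let a fraction c of AEs reach the dataset, the same in both arms. The proportion with at least one recorded AE is 1 − exp(−c × m).

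| Means m (two arms) | c | With at least one AE | Difference |
|---|---|---|---|
| 1.0, 1.5 | 1 | 63.2% v 77.7% | 14.5 points |
| 1.0, 1.5 | 0.5 | 39.3% v 52.8% | 13.4 points |
| 1.0, 1.5 | 0.25 | 22.1% v 31.3% | 9.2 points |
| 2, 3 | 1 | 86.5% v 95.0% | 8.6 points |
| 2, 3 | 0.5 | 63.2% v 77.7% | 14.5 points |

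For example, 1 − exp(−0.5 × 1.0) = 0.393 and 1 − exp(−0.5 × 1.5) = 0.528. Differences are taken before rounding. The absolute percentages fall sharply as capture falls. The ratio of mean counts stays at 1.5, because c multiplies both arms. The difference in percentages can shrink or grow with no differential recording at all. The illustration therefore shows under-counting, and not a distortion that favours one arm.

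**The case against.** The strongest reply is that the closing sentence of 9.3.3 is an outlier. It does not say the notes are the sole destination, and 9.3.3 introduces its list as events that are also reported in the eCRF. On that reading every AE goes on the log and the listed ones get an eCRF report as well. Table 1, Sections 6.2 to 6.4 and Section 9.2 all favour full recording. This stands to the extent that sites following those sections would lose nothing, so under-counting is possible rather than certain. It does not remove the conflict: no section states that reading, and none says that log entries outside the eCRF reach the analysis.

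Three stronger readings are tempting and are not supported.

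- *Non-serious steroid-class events never reach the analysis.* Oral infection and community pneumonia are listed in 9.3.3, and the Section 4.5 risk table requires every pneumonia diagnosis to be reported as an AE or SAE. The gap is narrower.
- *The comparison between arms is biased.* A site's recording rule applies to both its arms. Site is not a minimisation factor and the trial is open label, so chance imbalance or uneven discretion is conceivable. The documents show neither, and do not show that sites follow different sections.
- *Washout AEs are lost because the 9.3.3 list starts at Baseline.* That start governs the list. Section 9 runs from consent, Section 6.2 collects AEs at Visit 2, and Section 6.5 records exacerbations from washout.

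On exacerbations, 9.3.3 can be read as a specific exception to 9.3.2. Exacerbations also have their own record (Section 6.5) and analysis (SAP 4.5.8), so those data are not lost. What remains open is whether they enter the AE totals.

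**Conclusion.** The contradiction is real and should be corrected. If sites follow the last sentence of 9.3.3, non-serious AEs outside its list may be missing from the all-AE endpoint and the SAP 4.6 summaries. The likely effect is under-counting in both arms, by an amount the documents do not allow anyone to estimate. The AE status of exacerbations is also unsettled, which affects how the totals are read.

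The conclusion rests on two readings: that notes in 9.3.3 means notes in place of the log, as in 9.3.2, and that events held only in the notes are not retrieved for analysis, since no retrieval is described. The conflict of wording is certain; actual incompleteness depends on site practice. A descriptive safety endpoint is affected. The primary and efficacy analyses are not.

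**What to change.** 1. **Protocol 9.3.3:** reword the last sentence so that all AEs from consent to final follow-up go on the AE log/eCRF, in line with Sections 9 and 9.5. Keep the list as events of special interest.
2. **Protocol 9.3.2 and 9.3.3:** reconcile them so that one rule says whether a COPD exacerbation is recorded as an AE.
3. **SAP 4.6:** state which AE source is analysed and whether exacerbations are included in the counts.
4. **Before database lock:** have each site confirm which recording rule it followed and enter any AEs held only in the notes. If that cannot be done, label the AE tables as limited to the events captured.

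**Cost:** a protocol amendment, which under Section 12.1 needs ethics, regulatory and local R&D approval; a short SAP revision; and some extra AE log entry. The SAP is version 2.1, effective 27 June 2025, and describes some scoring as already done. Rewording alone will not recover events already left in the notes, so step 4 matters most for the results.
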